## 6.3. Visit Schedule

The study coordinator at the site should schedule the 30-day follow-up visit before the subject is discharged post-procedure. Obtain contact information for subject's significant other or caretaker(s) to ensure that subject will be able to comply with follow-up study visits. Study assessments to be performed at each visit are summarized in Table 1.

TABLE 1: Study Assessment Schedule	Visit 1 Day -1 -21 to -2 (Screen- ing & Baseline)	Visit 2 Day 0 (Treat- ment- dis charge)	Visit 3 30 (+/- 7) Days	Visit 4 60 (+/- 7) Days	Visit 5 (3 mo. +/- 2 wks) & Visit 7 (9 mo. +/- 2 wks)	Visit 6 6 months (+/- 2 weeks)	Visit 8 1 Year (+/- 4 weeks)	Visit 9  2 Year (+/- 4 weeks)
Written Informed Consent	1							
Baseline angiogram/images for screening	1							
Inclusion / Exclusion criteria assessment, including enrollment concurrence by an Independent Safety Committee that subject is not a candidate for conventional surgical or endovascular limb salvage procedures	1							
Demographic data, medical history, medication review, & physical exam	1							
Review of medications / dual anti-platelet regimen 	V	V	$\checkmark$		V	1	1	V
Rutherford Classification (RCC)	1		$\checkmark$		1	V	1	1
Wound healing assessment (completed or not), and photographs 	V		$\checkmark$		1	$\checkmark$	1	V
Index limb oxygenation measurement – TcPO2 	V		$\checkmark$		1	$\checkmark$	1	
Pulse evaluation via continuous wave doppler assessment of grafted area (proximal, graft, and distal to outflow vessels) 	√ (target location)	√8	~		1	V	V	1

TABLE 1: Study Assessment Schedule (cont)	Visit 1 Day -1 -21 to -2 (Screen- ing & Baseline)	Visit 2 Day 0 (Treat- ment- discharge )	Visit 3 30 (+/- 7) Days	Visit 4 60 (+/- 7) Days	Visit 5 (3 mo. +/- 2 wks) & Visit 7 (9 mo. +/- 2 wks)	Visit 6 6 months (+/- 2 weeks)	Visit 8 1 Year (+/- 4 weeks)	Visit 9  2 Year (+/- 4 weeks)
Serum Creatinine	√		$\checkmark$			$\checkmark$		
Numeric Pain Scale Rating (1-10) 	1		1		1	1	1	V
Procedural angiogram and device performance data		V						
Technical Success		4						
Procedural Success		1	1					
Procedure time, defined from sheath insertion to final catheter removal		V						
Fluoroscopy time and Contrast Load for the index procedure		V						
Device- or procedure-related AE/SAE's 		1	V		1	$\checkmark$	1	$\checkmark$
Assessment of amputation and/or major re- intervention of the Stent Graft			V		V	$\checkmark$	V	V
Duplex Ultrasound Exam to assess Stent Graft patency 			V	1	√9	1		
All-cause mortality			V		1	٦	V	$\checkmark$

 Dual antiplatelet therapy is required for 3 months post-procedure. At a minimum, all subjects must be started on

DAPT at least 1 week before procedure or adequately pre-loaded with DAPT as per institution practice.  Prior to any re-intervention of the stent graft, an angiogram/image and wound photograph should be obtained for adjudication purposes.

TcPO2 will be measured at 2 constant points on the dorsum of the midfoot through the 12 month follow-up.

 Per ACC/AHA 2006 Peripheral Arterial Disease Guidelines

 Review of any hospitalizations or procedures involving the index limb, and/or potentially related to the device or procedure; all SAEs through 6 months. For patients out of area or who refuse to come in for this visit, a telephone

assessment should be conducted to capture as much information as possible at this time point.

 May be performed at any visit as standard of care, as indicated by clinical symptoms.

 Continuous wave doppler must be performed between 4 and 30 hours post-procedure to assess for acute thrombosis; any findings of acute thrombosis must be reported to the Sponsor within 24 hours of the exam. The sponsor must notify the FDA via email of any cases of acute stent graft thrombosis within 5 days of the event.  3 Month visit only

## 6.4 Study Procedures

#### 6.4.1 Enrollment

Once any component of the LimFlow Stent Graft System is introduced into the body, the subject will be considered to be enrolled in the study and subject to all follow-up requirements. If the device is introduced but implantation is either not attempted or unsuccessful, subjects will be followed through 30 days for safety only, or through resolution or stabilization of any device- or procedure- related adverse events, whichever is longer. Those subjects will then be exited from the study and will not be replaced.

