# 6.6 Study Exit

Once the subject has a) completed the follow-up visits; b) has withdrawn consent to participate in the study; c) has met a primary study endpoint, or d) was enrolled but not able to have the device implanted, they will be exited from the study provided they do not have any conditions that require continued follow-up. The date of exit, reason, and subject status should be recorded.

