# 7.2 Secondary Safety Endpoint

Amputation-Free Survival at 6 months, defined as the percentage of subjects with:

- Limb Salvage: Freedom from above-ankle amputation of the index limb AND
- **Survival:** Freedom from all-cause mortality

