# **8.0 Statistical Considerations**

## 8.1 Analysis Populations and Data Handling Conventions

## 8.1.1. Safety

All subjects who receive any portion of the LimFlow Stent Graft System will be included in safety analysis, as Intent to Treat population (ITT).

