## 8.1.3. Missing Data

Missing data will not be imputed by any method. All subject data will be collected on standardized case report forms.

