#### 8.2.2. Safety

#### 8.2.2.1. Primary Safety Analysis

The primary safety analyses will be based on the 30-day incidence rate of Amputation-Free Survival for the safety study sample per 8.1.1. Survival rates, 95% confidence intervals, and Kaplan-Meier analyses will be reported.

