## 8.2.2.2. Secondary Safety Endpoints Analyses

The secondary safety endpoint will be similarly summarized as described in 8.2.2.1.

Additionally, all serious and non-serious adverse events that are potentially device- and/or procedure-related, and/or related to the index limb will be summarized by type of event, severity, relationship to the device and/or procedure, and timing of event relative to the procedure date.

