# **11.2.** Reporting of Serious and Non-Serious Adverse Events

## 11.2.1. General Reporting Requirements (Serious & Non-Serious Adverse Events)

All potentially device- and/or procedure-related adverse events (AE) and all serious adverse events (SAE) will be reported and monitored from the time of treatment through the 6 month follow-up visit. Any SAEs related to the index limb will be reported and monitored throughout the 2 year follow-up visit. The report should include: severity, duration, action taken, treatment outcome and

relationship of the adverse experience to the study device, procedure, concomitant medications, preexisting condition, etc. (i.e., unrelated, related or relationship unknown).

In the case of serious adverse events, procedure and/or device observations and malfunctions, medical record documentation (e.g. procedure notes, operative notes, discharge summary, relevant progress notes, imaging or lab studies) must be provided to sponsor or its designee.

The following criteria must also be adhered to by the investigator in the case of serious adverse events:

- The Adverse Event eCRF must be signed by the investigator.
- It is the responsibility of the investigator to inform their IRB of serious adverse events as required by their IRB procedures and in conformance with FDA and local regulatory requirements.

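### Failed-implant subjects belong, on the natural reading, to the 6-month amputation-free survival population but have no scheduled contact after about day 30, and the 6-month estimator is not named

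*Combined protocol and SAP*

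**What the plan says.** **Population.** Section 8.1.1: "All subjects who receive any portion of the LimFlow Stent Graft System will be included in safety analysis". Section 8.1.2 separately restricts the effectiveness analyses to subjects who were implanted.

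**Endpoint and analysis.** Section 7.2 sets "Amputation-Free Survival at 6 months, defined as the percentage of subjects with" no above-ankle amputation of the index limb and no death from any cause. Section 8.2.2.2: "The secondary safety endpoint will be similarly summarized as described in 8.2.2.1". Section 8.2.2.1 uses the 8.1.1 sample and adds: "Survival rates, 95% confidence intervals, and Kaplan-Meier analyses will be reported". Section 8.1.3: "Missing data will not be imputed by any method".

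**Follow-up.** Section 6.4.1 first treats a subject as enrolled, and bound by every follow-up requirement, once any component enters the body. It then says that if implantation is not attempted or fails, "subjects will be followed through 30 days for safety only", or until related adverse events resolve or stabilise if that takes longer. The subject then exits and is not replaced. Section 6.6(d) repeats the exit for subjects who could not be implanted: "they will be exited from the study provided they do not have any conditions that require continued follow-up". Section 6.6 also has the date, reason and status at exit recorded.

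**Event reporting.** Under 11.2.1, related adverse events and all SAEs "will be reported and monitored from the time of treatment through the 6 month follow-up visit". Index-limb SAEs are reported to 2 years. Section 11.1 counts as SAEs death from any cause and events that lead to lasting disability or an in-patient stay. The glossary agrees.

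**The concern.** The 6-month endpoint appears to cover subjects whom the visit plan stops observing about five months before it is measured. The reason observation stops is implant failure, which may itself be related to later limb loss or death. That differs from ordinary loss to follow-up.

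What is at stake is how the only secondary safety endpoint is read. Section 8.2.3.1 would report the proportion of subjects converted to other treatment after technical failure, but not how they fared by 6 months. A reader could not tell whether the 6-month figure reflects everyone in whom the device was used or, in effect, only those in whom it was implanted. The confidence interval would not show this.

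**Working it through.** The plan has no figure to reproduce. It gives up to 35 subjects (4.2) and at least 10 completed (8.3), with no technical-failure rate, expected AFS or target.

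**Step 1: who is in the population.** Section 8.1.1 speaks of receiving any portion of the system, and 6.4.1 of introducing any component. The words differ. Because 8.1.2 confines only effectiveness to implanted subjects, the natural reading is that failed implants are in the safety set.

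**Step 2: what follow-up they get.** The specific rule in 6.4.1, supported by 6.6(d), limits the general sentence before it. A failed-implant subject with no related adverse event and no other condition needing follow-up exits at about day 30. Table 1 checks amputation and mortality at 6 months, but nothing applies those checks to exited subjects. The telephone provision in its footnote 6 is for patients who are out of area or refuse the visit.

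**Step 3: what the analysis would do.** Kaplan-Meier, a recorded exit date and no imputation together point to censoring at exit. Section 7.2, however, defines a percentage of subjects, and 8.2.2.1 does not say whether the headline is the Kaplan-Meier estimate or a crude percentage, or over which denominator.

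**Step 4: how much is left open.** Let u be the number of failed implants who exit event-free and whose 6-month status stays unknown. With N = 35, the undetermined share is u/35:

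- u = 1: 1/35 = 2.9 points
- u = 2: 2/35 = 5.7 points
- u = 3: 3/35 = 8.6 points

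The values of u are assumed. With u = 0 the share is zero. If fewer than 35 are enrolled, the share is u/N and so larger.

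**Step 5: error of Kaplan-Meier with censoring at exit.** Let a be the number of implanted subjects event-free at day 30. Let ci and cf be the event-free probabilities from day 30 to 6 months for implanted and failed-implant subjects.

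- Kaplan-Meier = (a + u)/35 × ci
- Actual = (a × ci + u × cf)/35
- Error = u × (ci − cf)/35

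With ci assumed between 0.75 and 0.90 and cf anywhere from 1 to 0:

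- u = 1: −0.7 to +2.6 points
- u = 2: −1.4 to +5.1 points
- u = 3: −2.1 to +7.7 points

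The upper ends require every exited subject to have a later event. The error is zero when cf = ci.

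**Step 6: illustration, all inputs assumed.** Of 31 implanted subjects, 30 are event-free at day 30 and 25 at 6 months. Of 4 failed implants, 1 has an event by day 30 and 3 exit event-free.

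- Kaplan-Meier: 33/35 × 25/30 = 78.6%
- Known status only: 25/32 = 78.1%
- Confirmed event-free over all subjects: 25/35 = 71.4%
- Actual value if 0, 1, 2 or 3 of the three later have an event: 28/35 = 80.0%, 27/35 = 77.1%, 26/35 = 74.3%, 25/35 = 71.4%
- Kaplan-Meier error in that order: −1.4, +1.4, +4.3, +7.1 points

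**Step 7: sampling error.** Exact 95% intervals are 60.0 to 90.7% for 25/32 and 53.7 to 85.4% for 25/35, each about 31 points wide. The 8.6 points left open in this example are well below that.

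**The case against.** The strongest case is that the plan already covers most of this.

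- *Full follow-up is stated.* Section 6.4.1 says so for everyone in whom a component is introduced. The next sentences carve out failed implants and 6.6(d) confirms it, so this does not restore 6-month follow-up. It does show that the sentences need reconciling.
- *Both components of AFS are reportable.* This largely stands. Death is an SAE, and above-ankle amputation meets the lasting-disability criterion whether or not it involves an in-patient stay. Section 11.2.1 runs to the 6-month visit with no exclusion for failed implants, and 11.1 has unresolved SAEs followed up. It would therefore be wrong to infer that the plan makes no provision for learning of these events. What is missing is a scheduled contact, or a statement that reporting continues after exit. The body of 11.2.2 was not available for this review and may bear on this.
- *Censoring at exit is the obvious convention.* It is the likely default, so a reader should not infer that the plan leaves the matter wholly open. But the headline estimator is not named, and censoring triggered by implant failure cannot be assumed to be non-informative.
- *The consequence is limited.* This stands. The study is a single-arm pilot, the endpoint is secondary and descriptive, and no test or performance threshold depends on it.

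**Conclusion.** The point holds as a mismatch between the safety population, the exit rule and the 6-month endpoint, together with an unnamed estimator. It rests on reading 8.1.1 as including failed implants, and on 6.4.1's specific rule prevailing over its general one.

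The size cannot be derived from the documents and may be zero. With 35 enrolled it is up to 2.9 points per failed implant of unknown status, and 8.6 points for an assumed three. That is less than the sampling error.

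Two stronger readings are tempting and are not supported:

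- **That 6-month AFS will be overstated.** Section 1.3 says that this population will have a major amputation if the procedure is not attempted. That statement gives no time frame, and the exited group also includes attempted but unsuccessful implants. Worse outcomes are plausible but not established, and Step 5 shows that the error can have either sign.
- **That the 30-day primary endpoint is compromised.** A reader might infer this from the 7-day window around Visit 3. Section 6.4.1 follows these subjects through 30 days at least, so the primary endpoint is not affected.

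**What to change.** 1. **Reconcile the follow-up rules and secure 6-month status.** Bring the sentences of 6.4.1 into line with 6.6(d), 8.1.1 and 11.2.1, and say whether SAE reporting continues after exit. For failed-implant subjects, obtain vital status and index-limb above-ankle amputation status at 6 months by telephone or chart review. Table 1 footnote 6 already allows a telephone assessment for subjects who do not attend and could be extended to them.
2. **Name the 6-month analysis.** In 8.2.2.2, state the estimator, the denominator over all 8.1.1 subjects, and the censoring rule. Report the number of failed implants and the number with unknown 6-month status.
3. **Bound what stays unknown.** Report best-case and worst-case values as a sensitivity analysis (80.0% and 71.4% in the illustration), and amend 8.1.3 to allow it.

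The cost is about one or two contacts per failed implant and a protocol amendment with consent wording. No clinic visits or procedures are added. The reported 6-month AFS may be lower. If new contacts are not accepted, items 2 and 3 need only text changes to 8.2.2.2 and 8.1.3. They would make the uncertainty visible but would not remove it.

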#### 6.4.2. Intra-operative

At a minimum, all subjects must be started on dual anti-platelet therapy (DAPT) at least 1 week before the procedure or adequately pre-loaded with DAPT according to the institution's practice. For consented subjects that meet the pre-operative eligibility criteria, record the relevant data regarding their endovascular procedure. Record the following information:

- Target In-Flow Artery (cross-over point), including proximal reference vessel diameter (RVD) and assessment of calcification or any other abnormalities
- Target Out-Flow Vein (cross-over point) characteristics
- Intra-operative anticoagulants administered, and corresponding ACT levels
- Pre- and post-procedural angiographic images showing flow to the foot
- Procedure start and finish times
- Total contrast amount given
- Total fluoroscopy time for the procedure
- Documentation of any device- or procedure-related adverse events
- Technical Success

At the end of the endovascular procedure, with the procedural sheath in place and under fluoroscopic visualization, an injection of contrast will be made to assess the anatomy, placement and patency of the proximal, body and distal ends of the Stent Graft.

#### 6.4.3. Post-operative

After the LimFlow Stent Graft System is successfully placed, the access site and peripheral extremity should be closely monitored. Dual anti-platelet therapy should be prescribed for a minimum of 3 months post-procedure.

All subjects will undergo a continuous wave doppler exam of the stent graft between 4 and 30 hours post-procedure. The exam is intended to verify the patency of the LimFlow stent graft and assess for acute stent graft thrombosis. Any findings of acute stent graft thrombosis must be reported to Sponsor within 24 hours of the exam and reported as an adverse event. The sponsor must notify the FDA by email of any cases of acute stent graft thrombosis within 5 days of the event.

## 6.5 Follow-up

Subjects should return to the clinic at 30 and 60 days (+/- 7 days), at 3, 6, and 9 months (+/- 2 weeks), and then annually for up to 2 years following their endovascular procedure and the peripheral limb/wound should be assessed.

Routine surveillance of the wound and index limb will be performed during each follow-up visit, in accordance with ACC/AHA 2006 Peripheral Disease Guidelines. Examinations will include assessments of pulse, pain, Rutherford Classification, TCPO2, wound healing status, medication regimen and any procedures or complications related to the index limb occurring since the last visit. The limb/wound will be photographed, displaying a metric ruler in the frames, and in enough detail to capture any change in wound status. Photographs are to include Anterior-Posterior (AP) photos of the dorsum of the foot including toes, medial and lateral projections and plantar.

**Duplex Ultrasound Exam Guidelines:** A duplex ultrasound exam will be performed at 1, 2, 3, and 6 month visits to assess the following:

- Presence of any significant stenotic or occlusive lesions proximal to the AV fistula that may compromise in-flow
- Diameter of the stent graft proximal to the crossing point, just distal to the crossing point, proximal upper tibial, mid tibial and lower tibial
- Flow volume measurements based on Diameter and Time Averaged Mean Velocity (TAMV) at the identical points stated above where diameter measurements were made
- Presence of flow in the outflow veins of the foot and flow volume measurements if possible
- Standard duplex ultrasound of the tibial arteries with particular reference to the presence of reverse flow.

Subjects should be instructed to promptly notify the investigator regarding any outside surgical referrals initiated by referring physicians caring for the subject's wounds.

NOTE: In the event that an index limb is determined to need a re-intervention or major amputation, a photograph of the wound and angiogram/images should be collected prior to the procedure for event adjudication by the ISC.

# 6.6 Study Exit

Once the subject has a) completed the follow-up visits; b) has withdrawn consent to participate in the study; c) has met a primary study endpoint, or d) was enrolled but not able to have the device implanted, they will be exited from the study provided they do not have any conditions that require continued follow-up. The date of exit, reason, and subject status should be recorded.

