Follow-Up Schedule	Measures of safety and effectiveness will be assessed through hospital discharge, at 30 and 60 (+/- 7) days, at 3, 6, and 9 months (+/- 2 weeks), and at one year (+/-
	4 weeks) and 2 years (+/- 4 weeks) post-procedure. The study will be completed and closed after all subjects have either met a primary endpoint, or completed the 2 year follow-up requirements.
Primary Patient Population	In this first pilot study, the patients selected will be the "no hope" CLI patients, those that have been determined to be ineligible for conventional surgical or endovascular options due to severe vascular disease.

	· · · · · ·
Pre-Operative	1. Subject must be $\geq$ 21 and $\leq$ 95 years of age
Inclusion Criteria	2. Clinical diagnosis of symptomatic critical limb ischemia, defined as any of
	the following clinical assessments coupled with hemodynamic evidence of
	severely diminished arterial inflow of the index limb (e.g., absent pulse(s),
	TcPO2 < 30 mm Hg):
	a. Rutherford Classification 5, ischemic ulceration
	b. Rutherford Classification 6, severe ischemic ulcers or frank
	gangrene
	
 
Subject has been assessed by the principal investigator, and reviewed by the Independent Safety Committee (ISC), and it was determined that no conventional distal bypass surgical or endovascular therapy for limb salvage is feasible due to the absence of a suitable distal target artery.
 

	
 
Proximally, the Target In-flow Artery at the cross-over point must be treatable with a 3.5 – 4.0 mm stent after pre-treatment (by visual estimate), and be <50% stenosed.
 

	5. Prior stent(s) to the Target In-flow Artery are allowed.
	6. Planned minor amputation of target extremity within 30 days after the
	index procedure is allowed.
	7. Subject is willing and able to sign the informed consent form.
	8. Subject has an adequate support network to ensure that subject is
	compliant with medication regimen and follow-up study visits.
Pre-Operative	Subjects will be excluded from participating in this study if they meet any of the
Exclusion Criteria	following criteria prior to initiation of the endovascular procedure:
	Tonowing enterna prior to initiation of the endovasediar procedure.
	1. Concomitant hepatic insufficiency, thrombophlebitis, deep venous
	thrombus, or coagulation disorder.
	2. Pre-existing immunodeficiency disorder or receiving immunosuppressant
	therapy.
	3. Prior peripheral arterial bypass procedure above or below the knee which

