# 6.0 Study Procedures and Enrollment

## 6.1. Duration of Subject Participation

Subjects enrolled in the study will participate for up to 2 years (+/- 4 weeks).

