# 7.0 Assessment of Safety and Effectiveness

# 7.1 Primary Safety Endpoint

Amputation-Free Survival at 30 days, defined as the percentage of subjects with:

- Limb Salvage: Freedom from above-ankle amputation of the index limb AND
- **Survival**: Freedom from all-cause mortality

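### Section 6.6(c) ends participation when a subject has *met* a primary endpoint but never defines *met*; on the likelier reading, subjects amputated by day 30 leave alive while Table 1 and 11.2.1 still require their deaths and SAEs

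*Combined protocol and SAP*

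**What the plan says.** Section 6.6 gives four exit triggers: completed visits, withdrawn consent, and then "c) has met a primary study endpoint, or d) was enrolled but not able to have the device implanted". When one applies, "they will be exited from the study provided they do not have any conditions that require continued follow-up". Neither *met* nor the conditions that would hold a subject in the study are defined there or in the glossary.

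The synopsis (Follow-Up Schedule) closes the study "after all subjects have either met a primary endpoint, or completed the 2 year follow-up requirements". This sentence governs closure of the study, not exit of individuals, but it uses the same undefined idea.

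Section 7.1 names the single primary endpoint: "Amputation-Free Survival at 30 days, defined as the percentage of subjects with" both limb salvage and survival. It is a group percentage, stated as a favourable outcome.

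Other sections assume longer observation:
- Section 6.5 schedules visits through 9 months "and then annually for up to 2 years following their endovascular procedure", and 6.1 sets participation at up to 2 years.
- Table 1 has a row "All-cause mortality" ticked from 30 days through the 2-year visit.
- Section 11.2.1 requires all SAEs through the 6-month visit and index-limb SAEs through 2 years. It makes no exception for subjects who have exited.

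**The concern.** A percentage of subjects free of an event is not something that one subject meets, so sites must guess what triggers 6.6(c). If they take it to mean failure on the endpoint, the subjects who leave alive are those who lost the limb early. Section 1.1 gives people amputated for vascular disease a 30-day mortality of 9-15% and a 1-year survival of 60%. These treatment failures are the subjects whose later course a safety pilot most needs to record.

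The Independent Safety Committee (section 10.2) adjudicates deaths and advises on continuing the study from the safety data. Events that occur after exit may not reach it. The study is descriptive, with one arm and no success threshold, so what is at stake is the completeness of the safety record, not a hypothesis test.

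**Working it through.** **Reading the text.** No document figure needs reproducing; the point rests on how the sections fit together.

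| Reading of *met* | Who exits under 6.6(c) | Fit with the rest of the protocol |
|---|---|---|
| Success: alive with the limb at day 30 | Most subjects, at day 30 | Contradicts 6-month AFS (7.2), the 3- to 12-month endpoints (7.3), the visits in 6.5 and Table 1 |
| Failure by day 30 | Living subjects with a major amputation by day 30 | Fits the endpoint's time frame; conflicts with the Table 1 mortality row and 11.2.1 |
| Failure at any time | Also subjects amputated later | Not supported: AFS at 6 months and limb salvage at 3 to 12 months are secondary endpoints |

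**Do the safeguards close the gap?** The proviso in 6.6 turns on undefined conditions. Section 11.1 has the investigator follow SAEs that are already unresolved. Neither secures a new SAE or a death in an amputee whose earlier events have resolved.

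**Inputs for the size, all applied as assumptions.**
- 35 subjects, all implanted (maximum from 4.2).
- Mortality 20% at 6 months (1.1, given there as an upper figure).
- Foot preservation 71% at 1 year, 95% CI 64-77% (meta-analysis in 1.1).
- Constant, competing hazards.

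**Amputees alive at exit.**
- Death hazard: -ln(0.80)/182.5 = 0.001223 per day.
- Amputation hazard: -ln(0.71)/365 = 0.000938 per day.
- Sum: 0.002161 per day.
- Probability of amputation before death by day t: (0.000938/0.002161) × [1 - exp(-0.002161 t)].

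| Time | Probability | Of 35 | Range |
|---|---|---|---|
| 30 days | 2.7% | 0.95 | 0.7 to 1.2 |
| 6 months | 14.2% | 4.95 | 3.9 to 6.7 |
| 1 year | 23.7% | 8.3 | 6.6 to 11.5 |
| 2 years | 34.5% | 12.1 | 9.8 to 17.4 |

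The range takes foot preservation from 64% to 77% and 6-month mortality from 10% (assumed) to 20%. Only the first row matches the text of 6.6(c).

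**Deaths after exit.** The amputation density is integrated against 1 - S(time since amputation), where S is survival after amputation. Two versions of S come from section 1.1:
- Version A is piecewise exponential through 85-91% at 30 days, 60% at 1 year and 42% at 3 years.
- Version B is a constant hazard with half dead at 5 years, because 1.1 also says that nearly half die within 5 years.

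| Amputated by | Deaths by | Version A | Version B |
|---|---|---|---|
| Day 30 | 6 months | 0.22 to 0.25 | 0.06 |
| Day 30 | 2 years | 0.47 | 0.23 |
| 6 months | 2 years | 2.36 | 1.1 |

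Hand check of the day-30, 2-year row: about 715 days remain after amputation. Version A survival is then about 0.506, so 0.954 × 0.494 = 0.47. Version B survival is 0.5^(715/1825) = 0.762, so 0.954 × 0.238 = 0.23.

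Using the 20%-per-6-months hazard after amputation instead gives 0.56 (amputated by day 30) and 2.70 (amputated by 6 months) by 2 years.

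**The case against.** The strongest reply is that nothing need be lost. Section 11.2.1 has no exit exception, Table 2 requires the investigator to report a death during the investigation within 24 hours, and a site could treat those duties as conditions that require continued follow-up. This stands in part: the documents show conflicting instructions, not certain loss of data. But the proviso is undefined, Table 2 does not say whether it reaches a subject who has exited, and up to 7 sites could resolve the conflict differently.

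A reader might infer several stronger claims that the documents do not support:
- *That day-30 successes are meant to leave.* The literal words allow it, but the 6-month and later endpoints and the visit schedule show that it is not intended.
- *That every later amputee is exited.* Amputation after day 30 is not a primary-endpoint event. The counts of 5, 8 and 12 apply only if sites stretch the rule.
- *That AFS or limb salvage is biased.* An amputee has already failed both, so later events change neither.
- *That section 6.1 alone contradicts 6.6.* Its 2 years is a maximum. The conflict rests on Table 1 and 11.2.1.

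The size is also open to challenge. The background survival figures after amputation are hard to square with each other, and 5.1.2 excludes life expectancy under 12 months, so true mortality may be lower. After 6 months, SAEs unrelated to the index limb fall outside 11.2.1 for everyone. These points hold, and they keep the size small.

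**Conclusion.** The point holds as an undefined exit trigger that conflicts with the protocol's own safety collection, and it should be fixed. On the reading that best fits the text, about 1 of 35 subjects is exited alive by day 30. About 0.2 to 0.25 deaths would follow by 6 months (fewer under version B) and about 0.2 to 0.5 by 2 years. If sites extend the rule to later amputations, about 5 are exited by 6 months, 8 by 1 year and 12 by 2 years. Among those amputated by 6 months, about 1.1 to 2.4 die by 2 years.

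The counts rest on 35 implanted subjects, constant hazards and background rates from other populations, so they indicate scale only. That *met* is undefined and that the sections conflict does not depend on them.

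**What to change.** Reconcile the synopsis closing rule, Table 1, 6.6 and 11.2.1:
- Delete 6.6(c), and delete the alternative of having met a primary endpoint from the closing rule, so that neither success nor failure on the primary endpoint ends data collection.
- State that participation ends at death, withdrawal of consent, documented loss to follow-up, completion of follow-up, or non-implantation after the safety follow-up in 6.4.1.
- State that living amputees stay in follow-up to 2 years for vital status and for the SAEs that 11.2.1 requires. Where a visit is not possible, use telephone contact of the kind in Table 1 footnote 6, which now covers only patients who are out of area or refuse the visit.

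The cost is a wording change in two places, a sentence on amputees, and a small number of extra contacts. These concern about 1 subject on the strict reading and up to about 12 on the broad reading at the central rates. No endpoint definition or analysis changes.
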